9.7 Prior and Concomitant Medications

Prior medications are defined as any continuing or new medication used within 28 days before visit 1 and discontinued prior to the day of study drug administration. Concomitant medications are defined as any continuing or new medication taken from time of first dose of study drug (visit 3) or anytime thereafter until the end of the study. Type and dose of concomitant medications used for phosphate binder therapy will be collected on a separate eCRF page at each visit. Medication information will be collected through to the visit 28/ET visit. World Health Organization Drug Dictionary Enhanced version March 2018, Format C, or later will be used to code concomitant and prior medications. Prior and concomitant medications will be tabulated by treatment group using frequency counts and percents for each anatomical/therapeutic/chemical Class Level 2 and 4 and generic drug name. All medications recorded on the eCRF, including start and stop (or ongoing as of) dates, AE number (if applicable), indication, dose, unit, route, and frequency will be listed. For the purpose of inclusion in prior or concomitant medication tables, incomplete medication start and stop dates will be imputed and then categorized into prior or concomitant medication categories.

9.8 Analysis Endpoints

9.8.1 Primary Efficacy Endpoint

The primary estimand is the reduction of mean plasma iPTH by at least 30% from pre-treatment baseline. The primary efficacy endpoint is the proportion of subjects in the ITT population (age 8 to <18 years) attaining a mean decrease in plasma iPTH from pre-treatment baseline of $\geq 30\%$ compared to placebo in the EAP.

9.8.2 Primary Safety Endpoints

The primary safety endpoints are:

- AEs
- Laboratory parameters (clinical chemistry, hematology, urine chemistry and urinalysis)

- PEs
- VS
- 12-lead ECGs

9.8.3 *Pharmacokinetic Endpoints*

For the interim analysis, repeated-dose (steady-state) PK determinations will be performed in subsets of subjects in both Cohort 1 and Cohort 2 by analyzing intensive serum 25-hydroxyvitamin D₃ concentrations versus time recorded during dosing with CTAP101 Capsules (n=10) or placebo (n=5) in the last three days of the 12th week of treatment.

For the final analysis, repeated-dose (steady-state) PK determinations will be performed in both Cohort 1 and Cohort 2 by analyzing serum 25-hydroxyvitamin D₃ concentrations versus time recorded (a) during dosing with CTAP101 Capsules or placebo in the last three days of the 12th week of treatment and (b) after the last administered dose in each active treatment group.

The following PK parameters will be calculated using observed and baseline-adjusted serum 25-hydroxyvitamin D₃ concentrations: (a) AUC, C_{\max} , t_{\max} , and C_{ss} ; time to steady-state concentration (t_{ss}), and (b) $t_{1/2}$, CL/F, and Vd/F, as feasible. Relative exposure and dose proportionality will be examined, if possible.

9.8.4 *Secondary Endpoints*

The secondary endpoints of the study will be:

- Proportion of subjects in the PP population with a mean decrease of at least 30% in plasma iPTH from pre-treatment baseline in the EAP, in aggregate and by mean weekly study dose in the EAP
- Proportion of subjects in the ITT and PP populations attaining adequate serum total 25-hydroxyvitamin D (≥ 30 ng/mL) in the EAP, in aggregate and by mean weekly study dose in the EAP
- The time courses of mean absolute changes from pre-treatment baseline in serum total 25-hydroxyvitamin D and plasma iPTH
- Proportion of subjects who attain 2 consecutive plasma iPTH values ≤ 70 pg/mL
- PD effects on mean serum calcium (corrected), serum phosphorus, serum CaxP product, serum calcitriol, serum 24,25-dihydroxyvitamin D₃, and the urine calcium:creatinine ratio
- Proportion of subjects with hypercalciuria (>200 mg calcium/g creatinine)
- Proportion of subjects with hypercalcemia (2 consecutive visits with serum calcium >10.3 mg/dL)
- Proportion of subjects with hyperphosphatemia (2 consecutive visits with serum phosphorus >5.5 mg/dL deemed to be study drug related)

9.8.5 [REDACTED]

- [REDACTED]
- [REDACTED]
- [REDACTED]
- [REDACTED]
- [REDACTED]
- [REDACTED]
- [REDACTED]
- [REDACTED]

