Safety and tolerability will be evaluated in the safety population by AEs, PEs, VS, hematology and clinical chemistries, and ECGs.

Pharmacokinetic Endpoints:

For the interim analysis, repeated-dose (steady-state) PK determinations will be performed in subsets of subjects in both Cohort 1 and Cohort 2 by analyzing serum 25-hydroxyvitamin D₃ concentrations versus time recorded during dosing with CTAP101 Capsules (n=10) or placebo (n=5) in the last three days of the 12th week of treatment.

For the final analysis, repeated-dose (steady-state) PK determinations will be performed in both Cohort 1 and Cohort 2 by analyzing serum 25-hydroxyvitamin D₃ concentrations versus time recorded (a) during dosing with CTAP101 Capsules or placebo in the last three days of the 12th week of treatment and (b) after the last administered dose in each active treatment group.

The following PK parameters will be calculated using observed and baseline-adjusted 25-hydroxyvitamin D₃ concentrations: (a) area under the concentration curve (AUC), maximum concentration, (C_{\max}), time to maximum concentration (t_{\max}), and steady-state concentration (C_{ss}); and (b) $t_{1/2}$, clearance (CL/F) and volume of distribution (Vd/F), as feasible. Relative exposure and dose proportionality will be examined, if possible.

Secondary Endpoints:

Secondary efficacy endpoints include the proportion of subjects in the per-protocol (PP) population attaining a mean decrease in plasma iPTH of at least 30% from pre-treatment baseline during the EAP and the proportions of subjects in the ITT and PP populations attaining a mean serum total 25-hydroxyvitamin D of at least 30 ng/mL, in aggregate and by mean weekly study dose in the EAP. Additional secondary endpoints include the time courses of mean absolute changes from pre-treatment baseline in serum total 25-hydroxyvitamin D and plasma iPTH; PD effects on mean serum calcium (corrected), serum phosphorus, serum CaxP product, and the urine calcium:creatinine ratio; the proportion of subjects in each treatment group with hypercalciuria (>200 mg calcium/g creatinine), hypercalcemia (2 consecutive visits with serum calcium >10.3 mg/dL) or hyperphosphatemia (2 consecutive visits with serum phosphorus >5.5 mg/dL (ages 12 to <18 years) or >6.0 mg/dL (ages 8 to <12 years), deemed to be study drug related); and the proportion of subjects who attain 2 consecutive plasma iPTH values ≤ 70 pg/mL.

[REDACTED]

[REDACTED]

[REDACTED]

Additional Assessments:

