Secondary efficacy will be assessed in the PP population by comparing the proportions of subjects in each active treatment group attaining mean decreases in plasma iPTH of $\geq 30\%$ (from baseline) in the EAP to the corresponding proportion of subjects in the placebo group, and in the ITT and PP populations by comparing the proportions of subjects in each active treatment group attaining mean serum total 25-hydroxyvitamin D of ≥ 30 ng/mL in the EAP to the corresponding proportions of subjects in the placebo group, in aggregate and by mean weekly study dose in the EAP. Mean weekly dose in the EAP will be calculated for three groups of subjects: those receiving 0 mcg per day; those receiving >0 and ≤ 30 mcg per day; and, those receiving >30 mcg/day of calcifediol.

Primary safety analyses will be conducted in the ITT population, and the statistical summary will be descriptive and performed by treatment group. No inferential hypothesis testing will be performed on the safety parameters with the exception of serum calcium, serum phosphorus, serum CaxP product, and urine calcium:creatinine ratio.

Secondary safety analyses will compare the proportions of subjects with confirmed corrected serum calcium >10.3 mg/dL or confirmed serum phosphorus >5.5 mg/dL (ages 12 to <18 years) or >6.0 mg/dL (ages 8 to <12 years) (deemed to be study drug related) or serum confirmed CaxP product >55 (for Cohort 1) or >60 (for Cohort 2) between the CTAP101 Capsules and placebo treatment groups using the Cochran-Mantel-Haenszel test statistic (alpha=0.05) for overall safety in the multicenter results.

Descriptive statistics will be applied to evaluate patient reported palatability and acceptability.

Inclusion Criteria:

Each subject must meet the following criteria to be enrolled in this study:

1. Cohort 1: Be 12 to <18 years of age and have a body weight of ≥ 40 kg; Cohort 2: be 8 to <12 years of age and have a body weight of ≥ 20 kg.
2. Be diagnosed with stage 3 or 4 CKD at least six months prior to the screening visit, and have an estimated glomerular filtration rate (eGFR) of ≥ 15 to <60 mL/min/1.73m² at screening.
3. Be without any disease state or physical condition that might impair evaluation of safety or which, in the investigator's opinion, would interfere with study participation, including:
 - a. Serum albumin ≤ 3.0 g/dL;

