3 INVESTIGATIONAL PLAN

3.1 Overall Study Design and Plan

This is a phase 3, multi-center, randomized, double-blind, placebo-controlled study which will be conducted primarily or entirely within the US. The study will involve approximately 108 eligible subjects, balanced for gender and CKD stage, having ages of 8 to <18 years, SHPT, stage 3 or 4 CKD and VDI. Approximately 72 subjects having ages of 12 to <18 years will be enrolled initially (Cohort 1) and, after prior approval from the US FDA, another 36 subjects having ages of 8 to <12 years will be enrolled (Cohort 2). Subjects in both cohorts will be randomized in a 2:1 ratio into two treatment groups to receive a daily bedtime dosage of (a) CTAP101 Capsules, or (b) matching placebo for 26-weeks. Subjects in Cohort 1 who are assigned to treatment with CTAP101 Capsules will start dosing at 30 mcg/day (1 CTAP101 Capsule) and, at the end of 12-weeks of treatment, will undergo upward dose titration to 60 mcg per day (two CTAP101 Capsules) provided that (a) plasma iPTH has not decreased by at least 30% from pretreatment baseline, (b) serum calcium (corrected for albumin) is <9.8 mg/dL, (c) serum phosphorus is ≤5.5 mg/dL, and (d) serum total 25-hydroxyvitamin D is ≤65 ng/mL. The initial dosage in Cohort 2 will be determined based on an interim analysis of data obtained from Cohort 1, as described below. The efficacy of CTAP101 Capsules (compared to placebo) in treating SHPT will be assessed from multiple plasma iPTH and serum 25-hydroxyvitamin D levels obtained in the efficacy assessment period (EAP), defined as the last 6 weeks of the 26-week treatment period.

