5.3 Selection and Timing of Dose for Each Subject

Subjects in Cohort 1 will receive two capsules (CTAP101 Capsules and/or matching placebo capsules) every day at bedtime to achieve the targeted initial daily dose of 30 mcg of calcifediol (one CTAP101 Capsule plus one placebo capsule) or 0 mcg of calcifediol (two placebo capsules). Any food intake within 60 minutes of medication administration will also be recorded. At the end of 12 weeks of treatment, subjects assigned to active treatment will undergo upward dose titration to 60 mcg per day (two CTAP101 Capsules) provided that (a) plasma iPTH has not decreased by at least 30% from pretreatment baseline, (b) corrected serum calcium is <9.8 mg/dL, (c) serum phosphorus is \leq 5.5 mg/dL, and (d) serum total 25-hydroxyvitamin D is \leq 65 ng/mL. Subjects in Cohort 2 will receive a starting daily bedtime dose which will be determined on the basis of the interim analysis of data obtained in Cohort 1, and will undergo upward dose titration at the end of 12 weeks of treatment to a new daily dose that is two times higher than the starting dose, provided that (a) plasma iPTH has not decreased by at least 30% from pretreatment baseline, (b) corrected serum calcium is <9.8 mg/dL, (c) serum phosphorus is \leq 6.0 mg/dL and (d) serum total 25-hydroxyvitamin D is \leq 65 ng/mL.

In order to maintain blinding, subjects will receive periodic supplies of study drug in bottles of identical appearance, some labeled “Bottle 1” and some labeled “Bottle 2,” along with the same dosing instructions regardless of randomization group directing the subject to take one capsule from one bottle labeled “Bottle 1” and one bottle labeled “Bottle 2” every day at bedtime.

An unblinded medical monitor who will be part of the independent, unblinded DSMB will oversee study drug assignments and dose adjustments (see below) by IRS.

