9.10 Efficacy Analysis

9.10.1 *Primary Endpoint Analysis*

Primary efficacy will be assessed in the ITT population by comparing the proportions of subjects in each treatment group (CTAP101 Capsules versus placebo) attaining a mean decrease from baseline in plasma iPTH of $\geq 30\%$ in the EAP using the Cochran-Mantel-Haenszel test statistic (alpha=0.05) for overall efficacy of the multicenter results. Subjects who do not have at least two plasma iPTH determinations in the EAP will be deemed non-responders.

9.10.2 *Secondary Endpoint Analyses*

Secondary efficacy will be assessed in the PP population by comparing the proportions of subjects in each active treatment group attaining mean decreases in plasma iPTH of $\geq 30\%$ from baseline in the EAP to the corresponding proportion of subjects in the placebo group, and in the ITT and PP populations by comparing the proportions of subjects in each active treatment group attaining mean serum total 25-hydroxyvitamin D of ≥ 30 ng/mL in the EAP to the corresponding proportions of subjects in the placebo group, in aggregate and by mean weekly study dose in the EAP. Mean weekly dose in the EAP will be calculated for two groups of subjects: those receiving ≤ 30 mcg per day; and those receiving > 30 mcg/day. Secondary efficacy will also be assessed by the time courses of mean absolute changes from pre-treatment baseline in serum total 25-hydroxyvitamin D and plasma iPTH (i.e., continuous iPTH change); and pharmacodynamic (PD) effects on mean serum calcium (corrected), serum phosphorus, serum [REDACTED], and the urine calcium:creatinine ratio.

- [REDACTED]

The number (n, %) of subjects attaining two consecutive reductions in plasma iPTH values $\geq 30\%$ from baseline, as well as, the number (n, %) subjects with two consecutive plasma iPTH values ≤ 70 pg/mL will be compared between treatment groups.

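### PP iPTH response by dose class in the EAP should be descriptive only, because dose class is set by the subject's own week-12 iPTH response

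*Combined protocol and SAP*

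**What the plan says.** Section 9.8.4 attaches the by-dose breakdown directly to iPTH. For PP subjects, the criterion reads "at least 30% in plasma iPTH from pre-treatment baseline in the EAP, in aggregate and by mean weekly study dose in the EAP".

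Section 9.10.2 assesses secondary efficacy in PP "by comparing the proportions of subjects in each active treatment group attaining mean decreases in plasma iPTH of" 30% or more with placebo. It then turns to 25-hydroxyvitamin D (25D), and that clause ends "to the corresponding proportions of subjects in the placebo group, in aggregate and by mean weekly study dose in the EAP". The Synopsis places the by-dose phrase in the same position, after the 25D endpoint: "attaining a mean serum total 25-hydroxyvitamin D of at least 30 ng/mL, in aggregate and by mean weekly study dose in the EAP".

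Only one active arm is randomised. Section 3.1 states: "Subjects in both cohorts will be randomized in a 2:1 ratio into two treatment groups".

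For upward titration at the end of week 12, Section 5.3 sets four conditions. The first is "a) plasma iPTH has not decreased by at least 30% from pretreatment baseline". The others concern corrected calcium, phosphorus and total 25D.

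The dose classes differ between places. Section 9.10.2 says "Mean weekly dose in the EAP will be calculated for two groups of subjects": at or below 30 mcg/day, and above. The Synopsis (Statistical Analyses) says "Mean weekly dose in the EAP will be calculated for three groups of subjects: those receiving 0 mcg per day", followed by a class above 0 up to 30 and a class above 30.

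**The concern.** The grouping variable is an earlier reading of the endpoint: same analyte, same 30% threshold, same baseline. Subjects who had responded by week 12 stay in the lower class. The higher class is made up of subjects who had not. No comparable sorting takes place on placebo, so neither class has a randomised comparator.

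A table built this way can show the higher dose doing worse when the doses are equally effective, or hide a real benefit of the higher dose. At stake is how readers interpret dose in a paediatric trial. The text labels most safety summaries descriptive (Section 9.11) but puts no such label, and no caveat about response-driven dose, on this breakdown. Because Section 9.10.2 speaks of each active group when only one is randomised, it can be read as extending the comparison with placebo to the dose classes.

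**Working it through.** The plan gives no figure for the dose classes. Its related figure is the sample size in Section 9.2: 72 active and 36 placebo, 20% dropout, response 0.4 versus 0.1. After dropout, 72 × 0.8 ≈ 58 and 36 × 0.8 ≈ 29. Exact two-sided Fisher power at 58/29 is 85.5%, so the stated 80% for the randomised comparison is met, and this point does not alter it.

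**1. Correlation from the shared baseline.** Take independent errors of equal variance (set to 1), one week-12 value and four EAP values (Visits 19–22, Section 6.9).
- Mean of two baseline values (Section 9.4): covariance 0.5; variances 1 + 0.5 = 1.5 and 0.25 + 0.5 = 0.75; correlation 0.5/√(1.5 × 0.75) = 0.47.
- One baseline value: 1/√(2 × 1.25) = 0.63.

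A persistent subject effect would add to either figure.

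**2. Class response with no dose effect.** Week-12 and EAP response are treated as a bivariate normal pair with the same response rate p at both times and correlation ρ. A fraction e of week-12 non-responders meets the other titration conditions. The values of ρ and e are assumptions.

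| p | ρ | e | ≤30 class | >30 class |
|---|---|---|---|---|
| 0.4 | 0 | 1.0 | 40% | 40% |
| 0.4 | 0.3 | 0.8 | 47% | 32% |
| 0.4 | 0.5 | 1.0 | 60% | 27% |
| 0.4 | 0.7 | 1.0 | 70% | 20% |
| 0.1 | 0.3 | 0.8 | 13% | 9% |
| 0.1 | 0.5 | 1.0 | 32% | 8% |
| 0.1 | 0.7 | 1.0 | 47% | 6% |

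The third row can be checked by recombining the classes: 0.4 × 0.598 + 0.6 × 0.268 = 0.40, the overall rate. The split comes from sorting alone and vanishes at ρ = 0.

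**3. A second model.** Log-normal iPTH; mean of two baselines; one week-12 value sets the class; mean of four EAP values. Assumed inputs: CV 20–30%, subject shift SD 0–0.2, hold-back for calcium, phosphorus or 25D 0–40%, everyone starting at 30 mcg; 45 settings.
- Inert drug, 10% response: ≤30 class 13–41%, >30 class 5–6%.
- 40% response, equal effect at both doses: 47–69% and 18–26%.
- True dose effect, taken from the adult mean decreases of 20.2% and 32.0% in Section 1.13: log(0.68/0.798) = −0.160, so iPTH is a further 14.8% lower at 60 mcg. Overall active response is held at 40%. All subjects on 60 rather than 30 would gain 19–35 points. The observed difference, >30 minus ≤30, is −26 to +19 points. It lies below the true gain in all 45 settings and is inverted in 25.

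**4. If the classes were tested against placebo.** With an inert drug at 58/29, the second model has the ≤30 class falsely beating placebo in 3–46% of trials, against about 1–2% for a randomly drawn class of the same size. At an assumed PP set of 29/15 the range is about 2–19%. In the first model the aggregate comparison stays at 3.0–3.8% under the null.

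**5. Dose reductions.** From the table in Section 5.4, a 60 mcg subject has 240/7 = 34.3 mcg/day after three reductions and 180/7 = 25.7 after four. Only the fourth crosses 30, so reductions alone move few subjects between classes. Suspensions can also lower mean EAP dose; neither is modelled.

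**6. Class definitions.** Since 0 ≤ 30, the lower class in Section 9.10.2, read literally, contains the placebo subjects. The Synopsis separates them.

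**The case against.** **No test is clearly specified.** Section 9.8.4 lists only a proportion. In the Synopsis and Section 9.10.2 the by-dose phrase closes the 25D clause, and no test or alpha is named for iPTH by dose. This stands. A reader might infer that the plan prespecifies a comparison with a false-positive rate of up to 46%. The documents do not support that: the figure needs a test the text only arguably calls for, no hold-back at all, and a PP set of 58/29.

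**PP may be smaller.** Section 9.3.1 requires two baseline iPTH values and Section 9.4 averages Visits 2 and 3, but Visit 2 takes place only after washout (Section 7.1.2). Read literally, subjects without washout could leave PP. A smaller PP set lowers the testing figures but leaves the class rates unchanged. If those subjects are instead analysed on one baseline value, selection is stronger (0.63 rather than 0.47).

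**Hold-back could offset the selection.** Subjects kept at 30 mcg for calcium, phosphorus or 25D might respond poorly later. As an extreme, set all of them to 0% EAP response: the ≤30 class still exceeds the overall rate in 33 of 36 inert settings and 32 of 36 settings with 40% response. Every exception is at 40% hold-back.

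**The titration rule is disclosed, and detail is deferred.** Both are true; Section 9.1 leaves error-rate detail to a Statistical Analysis Plan, which may settle the label. But Section 9.1 ties its familywise rate to no named endpoint, and multiplicity control would not remove a selection bias. Stating the rule in Section 5.3 does not put the caveat beside the result.

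**Conclusion.** The point holds as one of analysis and reporting for a secondary endpoint. EAP dose class is selected on response, so iPTH response by class is not evidence about dose, and comparing a class with placebo is not protected by randomisation. The direction follows if week-12 and EAP changes are positively correlated and hold-back is roughly unrelated to later iPTH change. The size is illustrative: CV, subject shift, hold-back and PP numbers are assumptions, and Cohort 2's starting dose is not yet set.

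Two further readings go too far. The primary ITT comparison and the aggregate PP comparison of the randomised arms do not have this dose-class selection. Nor will the dose-response necessarily appear inverted: in 20 of the 45 settings with a true dose effect it is understated but not reversed.

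The two-class and three-class definitions contradict each other whatever inputs are assumed.

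**What to change.** 1. In Sections 9.8.4 and 9.10.2, state that iPTH response by EAP dose class is reported descriptively (n, %), with no p-values against placebo, and require a table note that dose after week 12 depended on iPTH response. Keep inference on the randomised arms.
2. In the Synopsis and Section 9.10.2, say whether the by-dose breakdown covers iPTH as well as 25D, and replace the reference to each active group with the single randomised active arm.
3. Reconcile the dose classes in Section 9.10.2 with those in the Synopsis so that 0 mcg is a separate class.

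The cost is wording only: no new data, and no change to sample size, alpha or any dosing rule. The sponsor forgoes a dose-class test for iPTH that randomisation does not support.

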9.9 Additional Assessments

Patient reported outcomes on palatability and acceptability.

9.10 Efficacy Analysis

9.10.1 *Primary Endpoint Analysis*

Primary efficacy will be assessed in the ITT population by comparing the proportions of subjects in each treatment group (CTAP101 Capsules versus placebo) attaining a mean decrease from baseline in plasma iPTH of $\geq 30\%$ in the EAP using the Cochran-Mantel-Haenszel test statistic (alpha=0.05) for overall efficacy of the multicenter results. Subjects who do not have at least two plasma iPTH determinations in the EAP will be deemed non-responders.

9.10.2 *Secondary Endpoint Analyses*

Secondary efficacy will be assessed in the PP population by comparing the proportions of subjects in each active treatment group attaining mean decreases in plasma iPTH of $\geq 30\%$ from baseline in the EAP to the corresponding proportion of subjects in the placebo group, and in the ITT and PP populations by comparing the proportions of subjects in each active treatment group attaining mean serum total 25-hydroxyvitamin D of ≥ 30 ng/mL in the EAP to the corresponding proportions of subjects in the placebo group, in aggregate and by mean weekly study dose in the EAP. Mean weekly dose in the EAP will be calculated for two groups of subjects: those receiving ≤ 30 mcg per day; and those receiving > 30 mcg/day. Secondary efficacy will also be assessed by the time courses of mean absolute changes from pre-treatment baseline in serum total 25-hydroxyvitamin D and plasma iPTH (i.e., continuous iPTH change); and pharmacodynamic (PD) effects on mean serum calcium (corrected), serum phosphorus, serum [REDACTED], and the urine calcium:creatinine ratio.

- [REDACTED]

The number (n, %) of subjects attaining two consecutive reductions in plasma iPTH values $\geq 30\%$ from baseline, as well as, the number (n, %) subjects with two consecutive plasma iPTH values ≤ 70 pg/mL will be compared between treatment groups.

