5.6 Method of Assigning Subjects to Treatment Groups

After signing the ICF, prior to any study-related activities, subjects will be assigned a site-generated, ascending subject identification number and will retain that number throughout the study. Should a subject be withdrawn from the study, the subject identification number will not be reassigned. Approximately 350 subjects will be screened to enroll approximately 108 subjects who meet the enrollment criteria.

An IRS will provide study treatment group assignments for these 108 subjects using the computer-generated randomization code provided by the IRS vendor. The randomization code will be stratified age group (8 to <12 years and 12 to <18 years) and balanced within each age group for gender and CKD stage (stages 3 and 4).

In Cohort 1 (ages 12 to <18 years), approximately 72 subjects, balanced for gender and CKD stage, will be randomized in a 2:1 ratio to active or placebo treatment, respectively. Ten (10) subjects will be randomly selected from the active group and five (5) subjects will be randomly selected from the placebo group for intensive PK evaluation during the last 3 days of the 12th week of treatment (prior to dose escalation). Twenty other subjects will be randomly selected for end of study PK evaluations from the active group, ten of which will be receiving an end of study dose of 30 mcg/day and the other ten will receiving an end of study dose of 60 mcg/day.

In Cohort 2 (ages 8 to <12 years), approximately 36 subjects, balanced for gender and CKD stage, will be randomized in a 2:1 ratio to active or placebo treatment, respectively. Ten (10) subjects will be randomly selected from the active group and five (5) subjects will be randomly selected from the placebo group for intensive PK evaluation during the last 3 days of the 12th week of treatment (prior to dose escalation). End of study PK evaluations will be made after 26 weeks of treatment. Twenty other subjects will be randomly selected for end of study PK evaluations from the active group, ten of which will be receiving an end of study dose of 30 mcg/day and the other ten will receiving an end of study dose of 60 mcg/day.

For both cohorts, an IRS will provide study treatment group assignments using the computer-generated randomization code.

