9.2 Determination of Sample Size

Sample size has been calculated (using Fisher's exact test statistics) to provide power of 80% for a two-sided, alpha 0.05 level test of equal proportions comparing the percentages of subjects attaining a mean decrease of at least 30% in plasma iPTH (averaged over the last 6 weeks of treatment) compared to baseline on daily dosages of CTAP101 Capsules (active) versus placebo. Assuming response rates of at least 0.4 (CTAP101 Capsules) versus 0.1 (placebo), and using a 2:1 ratio of CTAP101 Capsules:placebo subjects with an estimated 20% dropout rate over the course of the study, a sample size of approximately 108 subjects is required in the study with two-thirds apportioned to the 12 to <18 year age group (Cohort 1) and one-third apportioned to the 8 to <12 year age group (Cohort 2), allocated as 72 subjects to CTAP101 Capsules and 36 subjects to placebo.

No subject replacement is planned.

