All ECG values will be listed.

9.11.2 *Secondary Endpoint Analyses*

The number (n, %) of subjects with hypercalciuria (>200 mg Ca/g creatinine), hypercalcemia (two consecutive visits with serum calcium >10.3 mg/dL) or hyperphosphatemia (two consecutive visits with serum phosphorus >5.5 mg/dL deemed to be study drug related) or serum confirmed CaxP product >55 (for Cohort 1) or >60 (for Cohort 2) will be compared between the treatment groups (active versus placebo) using the Cochran-Mantel-Haenszel test statistic (alpha=0.05) for overall efficacy of the multicenter results; the Chi-square test or Fisher's Exact test will be used for reporting the results in the separate strata.

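### The primary CMH test names no strata; its only descriptor points to centre, which is neither a randomisation factor nor allowed for in the sample size, and at 15 or more sites power could fall below 80%

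*Combined protocol and SAP*

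**What the plan says.** - **Primary test.** Section 9.10.1, like the synopsis, compares responder proportions in the ITT population "using the Cochran-Mantel-Haenszel test statistic (alpha=0.05) for overall efficacy of the multicenter results". No stratification variable is named. Subjects with fewer than two iPTH values in the efficacy assessment period count as non-responders.
- **Safety tests.** Section 9.11.2 uses the same CMH wording for hypercalciuria, hypercalcemia, hyperphosphatemia and CaxP product. It then calls for chi-square or Fisher tests "for reporting the results in the separate strata", without defining those strata.
- **Meaning of stratum.** The only gloss in the analysis sections is in 9.11, where the strata for the safety summaries are age and gender groups.
- **Randomisation.** Section 5.6 stratifies the code by age group, "balanced within each age group for gender and CKD stage (stages 3 and 4"). Centre is not listed.
- **Sample size.** Section 9.2 uses Fisher's exact test "to provide power of 80% for a two-sided, alpha 0.05 level test of equal proportions". The inputs are: "Assuming response rates of at least 0.4 (CTAP101 Capsules) versus 0.1 (placebo"), "using a 2:1 ratio of CTAP101 Capsules:placebo subjects with an estimated 20% dropout rate over the course of the study", and "allocated as 72 subjects to CTAP101 Capsules and 36 subjects to placebo".
- **Not given.** The documents give no number of sites, no rule for pooling small sites and no statement on a continuity correction.

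**The concern.** A CMH test is defined by its strata. Here the primary test has none named, and the one word attached to it, multicenter, points to a factor that the randomisation and the sample size do not use. Two statisticians could run different primary tests from this text.

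The choice has consequences. About 108 subjects are randomised 2:1 with no site factor listed, so small sites will often hold one arm only. Under centre strata those subjects drop out of the primary comparison, and the 80% target may be missed. Age group also separates the two cohorts. The starting dose of Cohort 2 is set by the interim analysis and may differ from that of Cohort 1, so age group is a natural stratum for the pooled comparison.

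**Working it through.** **1. The plan's own figure.** Inputs from section 9.2: 0.40 versus 0.10, 2:1, two-sided 0.05, 80% power, 20% dropout. The pooled rate is (2 × 0.4 + 0.1)/3 = 0.3.

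- Placebo n without correction: [1.96√(1.5 × 0.3 × 0.7) + 0.842√(0.4 × 0.6/2 + 0.1 × 0.9)]² / 0.3² = 24.5, rounded up to 25, so 75 in all.
- With continuity correction: (24.5/4) × [1 + √(1 + 6/(24.5 × 2 × 0.3))]² = 29.3, rounded up to 30, so 90 in all. Then 90 × 1.2 = 108, the stated total.
- Exact check: if all 20% dropouts count as non-responders, the rates become 0.4 × 0.8 = 0.32 and 0.1 × 0.8 = 0.08. Fisher's exact test at 72:36 then has 81.3% power.

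The stated 108 and 80% are reproduced, for an unstratified test.

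**2. Why one-arm sites contribute nothing.** For stratum k with n subjects, n₁ active, n₀ placebo, m responders and a active responders, the CMH statistic is [Σ(a − n₁m/n)]² / Σ[n₁n₀m(n − m)/(n²(n − 1))]. If n₀ = 0, then n₁ = n and a = m, so both the difference and the variance term are zero. The same holds if n₁ = 0.

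**3. How often that happens.** With 2:1 allocation that ignores site, a site with n subjects has one arm with probability (2/3)ⁿ + (1/3)ⁿ: 56% for n = 2, 33% for 3, 21% for 4 and 14% for 5. If 108 subjects fall at random over K sites, the expected share of subjects in one-arm sites is (2/3)(1 − 1/K)³⁶ + (1/3)(1 − 1/K)⁷². For K = 30 this is 0.667 × 0.295 + 0.333 × 0.087 = 22.6%.

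**4. Power.** Simulated CMH test with 72:36 subjects and rates 0.32 versus 0.08. Sites are equally likely and have no site effect. K is assumed. Ranges span separate simulation runs.

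| Strata | Subjects in one-arm sites | Power, uncorrected | Power, continuity-corrected |
|---|---|---|---|
| 8 randomisation cells | – | about 84–85% | about 76–77% |
| Age group only | – | 84.4% | 77.1% |
| Centre, 10 sites | 1.5% | 81% | about 72% |
| Centre, 12 sites | 3.0% | 81% | 71% |
| Centre, 15 sites | 5.8% | 79–80% | 69–70% |
| Centre, 20 sites | 11.4% | 77% | 66% |
| Centre, 30 sites | 22.5% | 71–73% | 58–60% |
| Centre, 40 sites | 32.2% | 66–68% | 52–53% |

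The 8 cells are age × gender × CKD stage. Their sizes are assumed to be four of 72/4 = 18 and four of 36/4 = 9, each split 2:1. An unstratified chi-square has about 84% power, so the loss comes from centre strata and not from using CMH.

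**5. Sensitivity.**
- Skewed site sizes: 78.8% at 20 sites, 74.8% at 30 and 72.1% at 40.
- Site effect with SD 0.7 on the logit scale (assumed): 77.6% at 20 sites and 73.4% at 30.
- No dropout (0.40 versus 0.10), uncorrected: 90% at 15 sites, 89% at 20, 85% at 30 and 80% at 40, against 94% with randomisation cells.

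**The case against.** A reader might infer that the plan stratifies by centre, discards its randomisation factors and is therefore underpowered. The documents do not support that. Section 9.10.1 never says that centre is the stratum, and the phrase can equally mean the overall result pooled across sites. Section 9.11 describes strata as age and gender groups. Section 9.11.2 sets the overall CMH result against results in separate strata, which fits demographic strata at least as well. The randomisation factors are not named in the test; that is not the same as being ignored.

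The size of the loss is also conditional. No site count is given. At 10 to 12 sites power stays at about 81%, and with no dropout 80% holds to about 40 sites. The advantage of the randomisation strata is not a guarantee either: with a continuity correction they too fall short of 80%. No bias or type I error problem has been shown, and centre strata with a pre-specified pooling rule could be defended.

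These points stand, and they limit the claim. They do not supply the missing strata. Sections 9.1 and 9.6 defer details to a Statistical Analysis Plan, but on error rate and missing data, not on strata. The randomisation strata had higher power than centre strata at every site count tested, with or without the correction.

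**Conclusion.** The point holds in conditional form. The strata of the primary test are unspecified, and the most natural reading of the wording matches neither the randomisation nor the sizing. If centre is meant, power is about 81% at 10 to 12 sites, drops just below 80% at about 15 and reaches 66–68% at 40, against about 84–85% with the randomisation factors.

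These figures rest on assumed site counts, allocation that ignores site, an uncorrected CMH test and every dropout counted as a non-responder. A subject who leaves late may still have two iPTH values in the assessment period, so the real dilution may lie between the two dropout cases shown. It would be wrong to say outright that the plan loses its 80% power. If centre is not meant, the gap is still there: strata left open until after unblinding would leave the primary p-value open to choice. Both readings call for the same correction, which should be made.

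**What to change.** In the synopsis, 9.10.1 and 9.11.2, replace the multicenter wording with a CMH test stratified by a fixed, pre-specified set of the randomisation factors: age group, gender and CKD stage. Do not add a clause that keeps a factor only if cell sizes allow, because that would let the data choose the strata. State that no continuity correction is used; with one, these same strata give about 76–77% in the non-responder case. Define the separate strata in 9.11.2 in the same terms. Show results by centre descriptively only.

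The cost is a sentence or two in each of the three places, with no new data and no added subjects.
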